4.1 Study Objectives

4.1.1 Primary Objective

The primary objective is to assess the long-term safety of study drug(s) in subjects who were enrolled in Eisai-sponsored lenvatinib studies.

4.2 Overall Study Design and Plan

This is an open-label extension study to roll over eligible subjects from Eisai-sponsored lenvatinib studies. Subjects are enrolled in the rollover study for the purpose of long-term safety data collection. The transition from the parent study to the extension study would occur after the completion and evaluation of the primary endpoint of the parent studies or after all study data for the primary outcome measure were evaluated for the parent study. The parent study is defined as the Eisai-sponsored lenvatinib clinical study in which the subject was receiving lenvatinib either as monotherapy or as combination therapy, or was receiving any other comparator therapy.

The subjects willing to participate in the rollover study have to sign the informed consent form (ICF) for Study E7080-G000-604. The “End-of-Treatment” assessments in the parent study are to be completed and reviewed by the investigator prior to subject enrollment into Study E7080-G000-604. The eligibility for the rollover study is to be established based on meeting all inclusion and exclusion criteria described in Section 9.3 of the protocol. The intention is that the subject will not be without study drug during the transition from the parent study to the rollover study. The subjects in Study E7080-G000-604 should receive the first dose of the study drug the following day after the last dose of the study drug in the parent study. All treatment-emergent adverse events (TEAEs) and serious adverse events (SAEs), regardless of relationship to study drug or procedure, should be recorded beginning from the time the subject signs the rollover study ICF for up to 28 days after the last dose of study drug(s) (or $5 \times$ half-life of study drug[s], whichever is longer). SAE management and reporting requirements specific to study drugs will be addressed as per the instructions in the parent study protocol. Ongoing AEs in the parent study will remain ongoing at the time of discontinuation in the parent study, and the rollover study will capture only new or worsening TEAEs occurring after signing the rollover study ICF.

Screening period:

From approximately Day -30 to Day -1, subjects may remain on the parent study.

Subjects will be enrolled into the study under the following cohort definitions.

Cohort A: Subjects who received lenvatinib monotherapy or who crossed over from a comparator arm to receive lenvatinib monotherapy in their parent study will continue to receive lenvatinib monotherapy.

Cohort B: Subjects who received lenvatinib combination therapy or who crossed over from a comparator arm to receive lenvatinib combination therapy in their parent study will continue to receive lenvatinib combination therapy.

Cohort C: Subjects who received comparator treatment in their parent study will continue to receive comparator treatment, with the exception of subjects receiving placebo. Subjects who received placebo in their parent study and who were either not permitted to cross over or who opted not to cross over to active treatment will not be eligible to enroll in this study.

Treatment Phase:

During the Treatment Phase, subjects still on treatment will continue the same treatment they received upon discontinuation of the parent study. Subjects will remain on treatment in consecutive cycles as per the parent study protocol until disease progression, development of unacceptable toxicity, subject request, withdrawal of consent, discontinuation of Study E7080-G000-604 by the sponsor, use of non-permitted concomitant drugs, unacceptable noncompliance with the protocol, or if the subject is lost to follow-up.

This is a rollover open-label study with no control group. Subjects will enter the study at the same doses of study drug of lenvatinib or the combination regimen, or any other comparator therapy (except placebo), upon discontinuation of the parent study.

Discontinuation criteria are as follows: progression of disease, unacceptable toxicity, subject request, withdrawal of consent, termination of study by sponsor, use of non-permitted concomitant drugs, unacceptable non-compliance with the protocol, subject lost to follow-up. Subjects will be permitted to continue study drug(s) beyond initial disease progression as long as the treating investigator considers that there is continued clinical benefit after discussing with the sponsor and if the subject is tolerating the study drug(s).

5 DETERMINATION OF SAMPLE SIZE

This is a rollover open-label safety study; no formal sample size calculations were performed. It is expected that approximately 50 subjects will be initially rolled over to the study. It is anticipated that additional subjects may also roll over to the study in the future. Subjects who meet all of the inclusion criteria and none of the exclusion criteria, with no evidence of progressive disease, and who have tolerated study drug(s) in their parent study without significant toxicities will be rolled over to this study. Subjects with evidence of disease progression but who continue to derive clinical benefit, as determined by the

investigator, would require discussion with the sponsor on an individual case-by-case basis prior to enrollment in this study.

6 STATISTICAL METHODS

All descriptive statistics for continuous variables will be reported using mean, standard deviation (SD), median, Q1, Q3, minimum and maximum. Categorical variables will be summarized as number (percentage) of subjects.

6.1 Study Assessments

6.1.1 Demographics

Subject demographic information will be collected and recorded in the electronic case report form (eCRF). Demographic information includes age, sex, and race/ethnicity.

6.1.2 Medical History and Physical Examinations

Initial physical examination and any therapeutic area-specific assessments will be performed as per local standard of care or as clinically indicated. Results of these examinations will not be recorded in the eCRF and will not be summarized.

6.1.3 Efficacy Assessments

Tumor assessments will be performed as per local standard of care. Results of these assessments will not be recorded in the eCRF and will not be summarized.

6.1.4 Safety Assessments

Safety assessments will consist of monitoring and recording all TEAEs, including all Common Terminology Criteria for Adverse Events (CTCAE) v4.03 grades (for both increasing and decreasing severity), and SAEs. Long-term safety information will be collected at the time study drug is dispensed to the subject.

Monitoring of laboratory measurements, vital signs, and performance of electrocardiograms or physical examinations will be done per local standard of care or as clinically indicated.

6.2 Study Subjects

6.2.1 Definitions of Analysis Sets

The Safety Analysis Set is the group of subjects who received at least 1 dose of study drug(s).

6.2.2 Subject Disposition

The number of subjects enrolled, treated, and prematurely discontinued from study treatment will be summarized. The reason for study drug discontinuation will be summarized according to the categories in the eCRF.

6.2.3 Protocol Deviations

Not applicable.

6.2.4 Demographic and Other Baseline Characteristics

Demographic characteristics (age, sex, race, ethnicity) for the Safety Analysis Set will be summarized using descriptive statistics.

6.2.5 Prior and Concomitant Therapy

Concomitant medications are not collected in the eCRF. If the subject takes a concomitant medication in response to an AE, the AE will be recorded in the Adverse Events eCRF.

6.3 Data Analysis General Considerations

Descriptive statistics for continuous variables will include the number of subjects, mean, standard deviation (SD), median, Q1, Q3, and range (minimum, maximum). Categorical variables will be summarized by reporting the number and percentage of subjects. In most cases, the denominator for calculating percentages will be the number of subjects in the column header. Whenever a different subset is used to define the denominator, a footnote will be provided to describe the set of subjects to be used as the denominator. The reporting number of decimal places will be provided in the table shells.

6.4 Efficacy Analyses

Not Applicable

6.5 Safety Analyses

All safety analyses will be performed on the Safety Analysis Set.

6.5.1 Extent of Exposure

The length of time on treatment (months), and the quantity of study drug administered [dose intensity (mg/day)] will be summarized.

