The efficacy and safety of lenvatinib treatment has also been evaluated in the multicenter. randomized, double-blind, placebo-controlled Phase 3 trial E7080-G000-303 (SELECT trial) in patients with RR-DTC with documented disease progression within 13 months. Patients were stratified by age (≤ 65 , > 65 years), region and ≤ 1 prior VEGFR-targeted therapies and randomized 2:1 to lenvatinib or placebo arms (24 mg a day, 28-day cycle). The primary endpoint was PFS assessed by Independent Radiologic Review; the secondary endpoints included ORR (ie, complete response [CR] + partial response [PR]), OS, and safety. A total of 392 patients (63.0 years median age; 51.0% male) were randomized at over 100 sites in Europe, North and South America, and Asia. Patients in the lenvatinib arm had a significantly prolonged PFS (hazard ratio = 0.21, 95% confidence interval [CI] = 0.14-0.31; $P \le 0001$) with a median PFS for the lenvatinib arm of 18.3 months (95% CI = 15.1-not evaluable) vs the placebo arm: 3.6 months (95% CI = 2.2–3.7). The lenvatinib arm PFS benefit was observed in all predefined subgroups: median lenvatinib arm PFS for patients with prior vs no prior VEGF-therapy was 15.1 months (n=66) and 18.7 months (n=195). respectively; rates (n) of CRs for the lenvatinib arm vs placebo arm were 1.5% (4) and 0, respectively; PRs for the lenvatinib arm vs the placebo arm were 63.2% (165) and 1.5% (2), respectively. Median exposure durations for the lenvatinib arm vs the placebo arm were 13.8 months and 3.9 months, respectively; median time to lenvatinib response was 2.0 months. Median OS has not been reached; deaths for the lenvatinib arm were 71 (27.2%) and for the placebo arm were 47 (35.9%). The 5 most common lenvatinib treatment-related adverse events (AEs) (any grade) were hypertension (68%), diarrhea (59%), appetite decreased (50%), weight loss (46%), nausea (41%). The most common Grade \geq 3 lenvatinib treatmentrelated AEs (\geq 5%) were hypertension (42%), proteinuria (10%), weight loss (10%), diarrhea (8%), and appetite decreased (5%). The lenvatinib dose was reduced in 78.5% of patients and lenvatinib was discontinued due to AEs in 14.2% of patients (Schlumberger, et al., 2014). Based on the efficacy and safety information to date, patients with RR-DTC may benefit from lenvatinib treatment.

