In regards to efficacy and safety in RCC, the Phase 2 portion of Study E7080-G000-205 enrolled 153 patients with advanced or metastatic, clear- cell, RCC who had a history of receiving 1 prior VEGF agent. A total of 153 patients were randomized in a 1:1:1 ratio to receive treatment with lenvatinib plus everolimus, lenvatinib (24 mg once daily [QD]), or everolimus (10 mg QD). The safety profile for lenvatinib plus everolimus was consistent with the known toxic effects of each individual agent, with no unexpected TEAEs observed. The most common TEAEs of any grade in the lenvatinib plus everolimus arm were diarrhea and fatigue or asthenia. Grade 3 and 4 events occurred in fewer patients allocated singleagent everolimus (25 [50%]) compared with those assigned lenvatinib alone (41 [79%]) or lenvatinib plus everolimus (36 [71%]). The most common Grade 3 or 4 TEAEs in patients allocated lenvatinib plus everolimus was diarrhea (10 [20%]), in those assigned single-agent lenvatinib it was proteinuria (10 [19%]), and in those assigned single- agent everolimus it was anemia (6 [12%]). Two deaths were deemed related to study drug, 1 cerebral hemorrhage in the lenvatinib plus everolimus group and 1 myocardial infarction with single-agent lenvatinib (Motzer, et al., 2015a).

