In regards to efficacy and safety in unresectable HCC, lenvatinib has been evaluated in the Phase 3 study of "A Multicenter, Randomized, Open-Label, Phase 3 Trial to Compare the Efficacy and Safety of Lenvatinib (E7080) Versus Sorafenib in First-Line Treatment of Subjects With Unresectable Hepatocellular Carcinoma" (E7080-G000-304). This was a non-inferiority study of patients who had unresectable HCC with ≥ 1 measurable target lesion, Barcelona Clinic Liver Cancer stage B or C, Child-Pugh class A, Eastern Cooperative Oncology Group (ECOG) $PS \le 1$, and with no prior systemic therapy. Among 954 enrolled patients, 478 patients received lenvatinib while 476 received sorafenib and were randomized 1:1 to lenvatinib (body weight \geq 60 kg: 12 mg/day; < 60 kg: 8 mg/day) or the comparator arm of sorafenib 400 mg twice daily. The efficacy of lenvatinib has been demonstrated to be non-inferior in terms of OS, and achieved statistically significant and clinically meaningful improvements in PFS, time to progression (TTP) and ORR by modified RECIST as first line therapy for unresectable hepatocellular carcinoma. The TEAEs were consistent with the known lenvatinib safety profile. Most common lenvatinib TEAEs were hypertension (42%), diarrhea (39%), decreased appetite (34%), decreased weight (31%), and fatigue (30%) (Cheng, et al., 2017). As there are patients who are continuing treatment from several ongoing clinical studies of different phases in the lenvatinib program at Eisai, the "roll-over" study will allow those patients to continue to receive their treatments of lenvatinib as monotherapy or in combination regimen provided that they are deriving clinical benefit. Long-term safety will be assessed in patients in this study.

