9.2 Discussion of Study Design, Including Choice of Control Groups

Subjects will enter the study at the same doses of study drug of lenvatinib or the combination regimen, or any other comparator therapy (except placebo), upon discontinuation of the parent study. This is a roll-over open-label study with no control group.

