9.7.1.7 Extent of Exposure

The number of days on treatment, quantity of study drug administered, and the number of subjects requiring treatment interruption, and treatment discontinuation due to TEAEs will be summarized.

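### SAP 6.5.1 reports dose received only in mg/day, which cannot separate a subject's regimen and entry dose from the dose maintained during the roll-over study

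*SAP*

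**What the plan says.** - **Exposure measure.** SAP 6.5.1 summarizes months on treatment and dose: "the quantity of study drug administered [dose intensity (mg/day)] will be summarized". This puts into practice protocol 9.7.1.7, which plans "The number of days on treatment, quantity of study drug administered, and the number of subjects requiring treatment interruption". Neither document plans relative dose intensity or any other percentage of a planned or entry dose.
- **Columns.** SAP section 4 presents results for China, Rest of World and all subjects. SAP 6.5 and 6.5.1 mention neither cohort nor drug. Protocol 9.7.1.6 asks for every safety summary to be given separately by treatment group.
- **Dose at entry.** Protocol 9.2: "Subjects will enter the study at the same doses of study drug of lenvatinib or the combination regimen". Section 9.4.1 says the same and extends it to comparators other than placebo. No entry doses in mg and no list of contributing studies are given.
- **Cited parent-study starting doses (protocol section 7).** Thyroid phase 3: "randomized 2:1 to lenvatinib or placebo arms (24 mg a day, 28-day cycle". Renal phase 2 monotherapy arms: "lenvatinib (24 mg once daily [QD]), or everolimus (10 mg QD". Liver phase 3, by body weight: "12 mg/day; < 60 kg: 8 mg/day", against a "comparator arm of sorafenib 400 mg twice daily".
- **Other dose information.** Protocol 9.7.1.6 also plans a count of dose reductions and the time until the first one. SAP 6.5 carries over neither. SAP 6.5.2 keeps an overview count of subjects whose TEAEs led to interruption or dose reduction, and a subject listing of lenvatinib dosing.

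**The concern.** The only objective is long-term safety, so the adverse event rates have to be read against the dose subjects actually received and kept. An absolute mg/day figure combines three things: the regimen of the parent study, any reduction made before entry, and any reduction or interruption during the roll-over study. Only the third describes how well long-term treatment was sustained here. If parent studies with different doses feed the same column, a low mg/day could mean heavy dose reduction or simply a lower-dose regimen.

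Splitting by cohort does not remove the problem. Cohort A takes lenvatinib monotherapy subjects from any parent study, so subjects who began on 24, 12 or 8 mg can sit together. The regional columns are exposed in the same way if the regions draw on different tumor types.

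**Working it through.** The documents state no dose-intensity figure, so there is nothing of theirs to reproduce. The inputs are the cited lenvatinib starting doses of 24, 12 and 8 mg/day (protocol section 7). Starting doses stand in for entry doses, which are not given. All mixes and maintenance ranges below are assumptions.

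**1. Spread of starting doses.** 24/8 = 3.0 across the cited lenvatinib monotherapy regimens; 12/8 = 1.5 within the liver study.

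**2. The same mg/day at different levels of maintenance.**
- 8 mg/day received: 8/8 = 100%, 8/12 = 67%, 8/24 = 33%.
- 12 mg/day received: 12/12 = 100%, 12/24 = 50%.

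**3. Effect of mix alone.** Let w be the share of subjects on 24 mg, with the rest split equally between 8 and 12 mg (average 10 mg). With every dose fully maintained, mean = 24w + 10(1 − w):
- w = 0: 10.0
- w = 0.25: 13.5
- w = 0.5: 17.0
- w = 0.75: 20.5
- w = 1: 24.0 mg/day

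At w = 0.5 with everyone held at 60% of dose, the mean is 0.6 × 17.0 = 10.2 mg/day. That is almost the same as the 10.0 mg/day of a fully maintained group with no 24 mg subjects.

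**4. How much of the variation is starting dose?** Write mg/day = D × R, with D the starting dose and R the fraction maintained. If D and R are independent, Var(log mg/day) = Var(log D) + Var(log R), and the share due to starting dose is Var(log D) / [Var(log D) + Var(log R)]. Take R as uniform from a lower limit a up to 1, with a from 0.3 to 0.7. Then Var(log R) is 0.1125 at a = 0.3 and 0.0105 at a = 0.7.

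| Assumed mix of 8/12/24 mg | Var(log D) | Share due to starting dose, a = 0.3 to 0.7 | Correlation of mg/day with R, a = 0.3 to 0.7 |
|---|---|---|---|
| Equal thirds | 0.206 | 65% to 95% | 0.54 to 0.22 |
| 45/45/10 | 0.109 | 49% to 91% | 0.59 to 0.24 |
| 50/50/0 | 0.041 | 27% to 80% | 0.83 to 0.45 |

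Example for the first row: 0.206/(0.206 + 0.1125) = 65%, and 0.206/(0.206 + 0.0105) = 95%. The correlations come from simulation under the same assumptions.

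**5. Reductions before entry.** In the thyroid phase 3 study, 78.5% of lenvatinib patients had a dose reduction (protocol section 7). A subject who started on 24 mg, entered on 12 mg and stayed there has kept 12/12 = 100% of the entry dose but 12/24 = 50% of the starting dose. The figure of 12 mg/day shows neither.

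**The case against.** - **A reader might infer that milligrams of sorafenib and lenvatinib will be averaged in one column.** No passage plans that. Protocol 9.7.1.6 calls for separation by treatment group, the SAP's dosing listing is specific to lenvatinib, and the table shells and derivation rules sit in separate documents not available here. What stands is only that the SAP does not itself state the split. A mixture of comparators inside Cohort C is likewise an assumption: sorafenib, for China, is the only comparator that section 9.4.1 names.
- **A reader might take the 3-fold spread as the spread at entry.** The figures are starting doses from studies described in the Introduction. The real spread at entry could be smaller or larger, because the contributing studies are not listed and doses may already have been reduced.
- **A reader might conclude that mg/day says nothing about dose maintained.** That goes too far. With only 8 and 12 mg starting doses, the correlation above is 0.45 to 0.83. The TEAE overview count and the lenvatinib listing add further information.
- **The full set of descriptive statistics would reveal a mixture.** SAP 6 and 6.3 require SD, median, quartiles and range, so a spread of doses would be visible. Its cause would not be: a minimum of 8 mg/day could be an unreduced 8 mg subject or a 24 mg subject reduced to a third.
- **This is a small descriptive study.** About 50 subjects are initially expected, no regional test is planned, and SAP version 2.0 deliberately cut outputs. This limits the weight of the point but does not answer it, since one added summary line is a small burden.

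**Conclusion.** The point holds in a limited form. As written, SAP 6.5.1 has one summary of dose received, in absolute mg/day, with no denominator and no stated split by drug. For lenvatinib, that summary cannot separate regimen and entry dose from dose maintained during the roll-over study, whether overall, by region or within Cohort A. Under the assumed mixes, starting dose accounts for between 27% and 95% of the log-scale variation, and mix alone can move a fully maintained mean from 10 to 24 mg/day.

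These sizes rest on the cited starting doses being represented among the subjects, on the assumed mixes, and on maintenance being independent of starting dose. If all lenvatinib subjects came from one regimen and entered on one dose, the problem would largely disappear.

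The regional concern is an inference. Sorafenib is the comparator named for China and is also the comparator in the cited 8/12 mg liver study, so a China versus Rest of World gap in mg/day could reflect tumor type. The documents do not state the regional mix. The defect affects how a descriptive safety report can be interpreted; it does not invalidate the adverse event tables.

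**What to change.** In SAP 6.5.1:
1. Summarize dose separately for each study drug and by treatment group, as protocol 9.7.1.6 requires, alongside the regional columns. Never pool across drugs. In Cohort B, report lenvatinib and its partner drug on separate lines.
2. Beside mg/day, add relative dose intensity: mean daily dose received during the roll-over study as a percentage of the subject's dose at roll-over entry. Define entry dose explicitly, for example from the first dosing record in this study, and state the planned-dose period for any drug not given daily.
3. Optionally, where parent-study data can be linked, add the percentage of the parent-protocol starting dose, labelled as including reductions made before entry.

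Items 1 and 2 need SAP wording and one derived variable, since protocol 9.4.1 already has administered drug recorded on the CRF. Some drug-by-group cells will be small. Item 3 costs more: it needs each subject's parent regimen and, for liver subjects, body weight. Neither is among the demography items in protocol 9.5.1, and under 9.5.7.6 weight is not routinely recorded. That is why it should stay optional.

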6.5.2 Adverse Events

The adverse event (AE) verbatim descriptions (investigator terms from the eCRF) will be classified into standardized medical terminology using the Medical Dictionary for Regulatory

Activities (MedDRA). The linked MedDRA preferred term (PT) and primary system organ class (SOC) are also captured in the database.

AEs collected in this study must be treatment-emergent adverse events (TEAE). This is defined as an AE that emerges during treatment in the rollover study, having been absent before the time the subject signs the rollover study ICF or

- Re-emerges during treatment in the rollover study, having been present before signing the ICF but stopped before signing the ICF, or
- Worsens in severity during treatment in the rollover study relative to the pre-ICF state, when the AE is continuous.

Only those AEs that are treatment emergent will be included in summary tables. TEAEs are those occurring on or after the first dose date of study drug and on or before 28 days after the last dose of study drug. All TEAEs will be presented in subject data listings.

An overview table, including the number and percentage of subjects with TEAEs, SAEs, deaths, and those with TEAEs that led to study drug discontinuation, interruption, or dose reduction will be provided. The number (percentage) of subjects with TEAEs will be summarized by SOC and PT, by relationship to study drug (Yes [related] and No [not related]), and by CTCAE toxicity grade as follows:

- Overview of TEAEs
- TEAEs by SOC and PT
- TEAEs by decreasing frequency of PT
- TEAEs with CTCAE Grade ≥ 3 by decreasing incidence of PT
- Treatment-emergent serious AEs by decreasing incidence of PT
- Overview of treatment-related TEAEs
- Treatment-related TEAEs by SOC and PT
- Treatment-related TEAEs by decreasing frequency of PT
- Treatment-related TEAEs with CTCAE Grade ≥ 3 by decreasing incidence of PT
- Treatment-related treatment-emergent serious AEs by decreasing incidence of PT
- Fatal TEAEs by decreasing incidence of PT
- TEAEs leading to treatment discontinuation of lenvatinib

The following listings will be provided for the subjects in the Safety Analysis Set:

- Demographics

- Disposition
- Lenvatinib dosing
- All AEs
- All SAEs
- Adverse events with CTCAE Grade 3 or above
- All AEs leading to study drug discontinuation
- All fatal AEs

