9.5.7.1 Adverse Events

An adverse event (AE) is any untoward medical occurrence in a patient or clinical investigation subject administered an investigational product. An AE does not necessarily have a causal relationship with the medicinal product. For this study, the study drug(s) is/are lenvatinib, or lenvatinib combination regimen, or any other comparator therapy (except placebo) as per the parent study.

AEs collected in this study must be treatment-emergent adverse events (TEAE). This is defined as an AE that emerges during treatment in the roll-over study, having been absent before the time the subject signs the roll-over study ICF or

- Re-emerges during treatment in the roll-over study, having been present before signing the ICF but stopped before signing the ICF, or
- Worsens in severity during treatment in the roll-over study relative to the pre-ICF state, when the AE is continuous.

The criteria for identifying TEAEs in this study are:

- Any unfavorable and unintended sign (including an abnormal laboratory finding), symptom, or disease temporally associated with the use of an investigational product, whether or not considered related to the investigational product
- Any new disease or exacerbation of an existing disease.

- Any deterioration in nonprotocol-required measurements of a laboratory value or other clinical test (eg, ECG or x-ray) that results in symptoms, a change in treatment, or discontinuation of study drug
- Recurrence of an intermittent medical condition (eg, headache) not present pretreatment (Baseline)
- An abnormal laboratory test result should be considered a TEAE if the identified laboratory abnormality leads to any type of intervention, withdrawal of study drug, or withholding of study drug, whether prescribed in the protocol or not

A laboratory result should be considered by the investigator to be a TEAE if it:

- Results in the withdrawal of study drug
- Results in withholding of study drug pending some investigational outcome
- Results in an intervention, based on medical evaluation (eg, potassium supplement for hypokalemia
- Results in any out-of-range laboratory value that in the investigator's judgment fulfills the definitions of a TEAE with regard to the subject's medical profile

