2 VERSION HISTORY

Version	Description	Date
1.0	Initial version	05 Jun 2019
2.0	
Revised the scope of the statistical analysis plan to reflect the decision by the team to prepare only 1 clinical study report which would present all analyses by region (China, Rest of World).Clarified that adverse events are considered treatment emergent in this rollover study if they occurred on or after the first dose date of study drug and on or before 28 days after the last dose date of study drug.Reduced the number of TLGs to only present major adverse event categories, eg, TEAEs, treatment-related TEAEs, SAEs, AEs CTCAE Grade ≥ 3, AEs leading to discontinuation.	28 Feb 2024

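### The three-part TEAE definition misses an AE that is ongoing at the roll-over ICF, resolves and then recurs, while the SAP date window counts it; nothing says which rule governs

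*SAP*

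**What the plan says.** SAP 6.5.2 gives three ways in which an AE can be treatment-emergent.

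- Limb 1, new event: it emerges on roll-over treatment, "having been absent before the time the subject signs the rollover study ICF".
- Limb 2, recurrence: "Re-emerges during treatment in the rollover study, having been present before signing the ICF but stopped before signing the ICF, or".
- Limb 3, worsening: "Worsens in severity during treatment in the rollover study relative to the pre-ICF state, when the AE is continuous".

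Protocol 9.5.7.1 and 9.7.1.8 carry the same limbs; limb 2 in 9.5.7.1 reads "Re-emerges during treatment in the roll-over study, having been present before signing the ICF but stopped before signing the ICF, or". The definition does two jobs. Protocol 9.5.7.1 and SAP 6.5.2 both limit AE collection to TEAEs, and SAP 6.5.2 admits only TEAEs to the summary tables.

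After the limbs, SAP 6.5.2 adds a date window: "TEAEs are those occurring on or after the first dose date of study drug and on or before 28 days after the last dose". The version history (SAP section 2) presents this as a clarification, under which "adverse events are considered treatment emergent in this rollover study if they occurred on or after the first dose date of study drug" and within the 28-day limit. Protocol 9.7.1.8 has no such window.

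Protocol 9.5.7.1 also lists criteria for recognising a TEAE. The only one that names recurrence is "Recurrence of an intermittent medical condition (eg, headache) not present pretreatment (Baseline"). Others cover unfavourable signs or symptoms associated in time with the product, worsening of a disease already present, laboratory results that lead to intervention or to stopping or withholding drug, and laboratory rises of at least 2 grades over the pre-ICF state (for five named tests, only if judged clinically significant).

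**The concern.** The limbs are meant to count new events, recurrences and worsening. The cut at the ICF in limb 2 works for episodes that ended before it. It leaves out an episode that was still running at the ICF, ended later and came back.

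The result is not coherent. A Grade 3 return counts if the earlier episode ended the day before the ICF. A Grade 1 event that climbs to Grade 3 without a break also counts. The same Grade 3 event after a break that began once the ICF was signed meets no limb.

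This matters because long-term safety is the only objective, and subjects enter still receiving at least one parent-study drug. Events ongoing at the ICF may well be toxicities of that drug, and their return after resolution is part of what the study is there to describe. If the limbs govern, such a return stays out of the TEAE tables. If the date window governs, it enters. If the site never records it, the choice of rule no longer matters.

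**Working it through.** The plan states no figure to reproduce. The check is to apply each rule literally to constructed AE histories.

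**Assumed timing** (illustrative): ICF on day −20, within the screening period of about day −30 to day −1; first roll-over dose on day 0; last dose on day 300.

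**Rules as coded**, for the episode under test:
- Limb 1: starts on treatment, and the AE was not present before the ICF.
- Limb 2: starts on treatment, the AE was present before the ICF, and the earlier episode stopped before day −20.
- Limb 3: the AE was present before the ICF, has run without a break, and reaches a higher grade on treatment.
- Date window: onset from day 0 to day 300 + 28 = day 328. For continuous worsening, the date of worsening is taken as onset.

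| History | Limb 1 | Limb 2 | Limb 3 | Date window |
|---|---|---|---|---|
| 1. New AE, day 50 | yes | no | no | yes |
| 2. Stopped day −40, returns day 50 | no | yes | no | yes |
| 3. Continuous, Grade 1 to 3 on day 50 | no | no | yes | yes |
| 4. Continuous since day −100, same grade | no | no | no | no |
| 5. Ongoing at ICF, stops day −10, returns day 50, same grade | no | no | no | yes |
| 6. As 5, returns at higher grade | no | no | no | yes |
| 7. Ongoing at ICF, stops day 30, returns day 50, same grade | no | no | no | yes |
| 8. As 7, returns at higher grade | no | no | no | yes |
| 9. Ongoing at ICF, stops day −15, returns day −5 | no | no | no | no |

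The limbs and the window agree on histories 1 to 4 and 9. They disagree on 5 to 8, which are exactly the histories with resolution after the ICF and return on treatment. Grade makes no difference, because limb 3 requires continuity. The histories were chosen to separate the rules, so 4 of 9 is not a rate.

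**Collection.** For histories 5 to 8, the recurrence criterion in protocol 9.5.7.1 does not help, since the condition was present at baseline. Protocol 9.1 leaves parent-study AEs open at the end of that study and captures only new or worsening events. A same-grade return can be judged neither. A higher-grade return (6 and 8) can reasonably be entered as worsening of an existing disease, and a laboratory rise from Grade 1 to Grade 3 is 3 − 1 = 2 grades, which meets the laboratory criterion apart from the five exceptions. Serious events are recorded from the ICF onward whatever their relationship to drug (protocol 9.5.7.1 and 9.5.9.1).

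**The case against.** The strongest reply is that the date window settles the matter. It follows directly after the sentence on what enters the tables, and the version history words it as a sufficient condition. On that reading every recorded recurrence with onset in the window is a TEAE. A reader might infer from the limbs alone that these recurrences are not TEAEs and disappear from the tables; the documents do not support so flat a conclusion. Yet the window can also be read as a time limit on events that already meet a limb. The SAP calls it a clarification, its section 8 expects no change to planned analyses, and the protocol's definition has no window. The conflict stands.

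Second, the other criteria in 9.5.7.1 carry no continuity condition and can catch many higher-grade returns. Serious events are collected anyway, and recorded events should appear in the planned AE listings. This stands, and it narrows the collection risk to mainly same-grade, non-serious, non-laboratory recurrences.

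Third, a site may treat a return after full resolution as a new AE under limb 1, and rules for linking episodes may sit in the CRF Completion Guidelines or dataset specifications, which are not part of these documents. That is possible, but neither the protocol nor the SAP says so, and the text of limb 1 points the other way.

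Fourth, a reader might try to size the loss for one event term as p × q, with p the share of subjects in whom it is ongoing at the ICF and q the share of those who resolve and recur. Assuming 10% to 50% for each gives 0.1 × 0.1 = 1 to 0.5 × 0.5 = 25 percentage points. Neither share is in the documents, and the product sets the effect of the date window and the other criteria to zero. The 68% hypertension and 59% diarrhea in protocol section 7 are treatment-related incidences at any time in an earlier phase 3 trial, not prevalence at roll-over. Subjects here must also have tolerated drug without significant toxicity (protocol 9.3).

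**Conclusion.** The point holds as a gap in the definition and an unresolved conflict between two rules. An AE ongoing at the ICF that resolves and then recurs on treatment meets no limb. The SAP window counts it if onset falls from first dose to 28 days after last dose, and nothing ranks the two. There is also a collection risk, since the window cannot recover an event that was never entered. That risk depends on sites applying the limbs literally, which the documents neither confirm nor rule out.

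The size cannot be estimated, because the documents contain no AE counts. A general downward bias in the reported TEAE rates is not shown; it would require that the limbs govern or that events go unrecorded. The change is still worth making, because TEAE status decides what enters the tables for the study's only objective.

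**What to change.** 1. Reword limb 2 in SAP 6.5.2 and protocol 9.5.7.1 and 9.7.1.8 so that it covers any AE that returns on roll-over treatment once it has resolved, whether it resolved before or after the ICF was signed.
2. State in SAP 6.5.2 that a recurrence after resolution is a new episode, classified by its own onset date, and that this rule governs where the limbs and the date window disagree.
3. Align the recurrence criterion in 9.5.7.1 and the CRF Completion Guidelines.

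With these in place limb 3 can keep its continuity condition, because a higher-grade return after a break is a new episode under limb 2.

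The SAP change is a few lines, and recorded recurrences need at most reclassification. Reported TEAE rates may rise slightly, and some sites may need queries. SAP version 2.0 is dated 28 Feb 2024 and its introduction describes study conduct in the past tense, so new protocol and guideline wording may come too late for some subjects. Recurrences never entered may not be recoverable, and the study report should say so.
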